8.4.6.1 Reporting a Pause

If a pausing criterion is met, a description of the AE(s) or safety issue must be reported by the PI within 1 business day to the CSO and the IRB according to their requirements. The PI will also notify the DSMB and FDA. In the event of a SUSAR, the FDA will also be notified by sponsor.

8.4.6.2 Resumption Following a Pause

The CSO, in collaboration with the PI and DSMB, will determine if study activities, including agent administration and/or other study interventions, may be resumed, and any additional modifications or requirements that may apply, for the impacted subject(s), or whether the events that triggered the pause require expansion to a study halt (see section 8.4.6).

The CSO or sponsor designee will notify the PI of the decision. The PI will notify the IRB of the decision according to the IRB's process.

8.4.6.3 Discontinuation of Study Agent

Subjects who received study agent/study intervention will continue to be followed for protocol-specified safety assessments or as clinically indicated, whichever is more conservative, during a study pause.

8.4.7 Halting Rules for the Protocol

"Halting" is discontinuation of study intervention/treatment/dosing (agent/placebo/procedure, etc.) for all subjects in a study and suspension of enrollment until a decision is made to either resume or permanently discontinue such activity. Subjects continue to be followed for safety during a halt.

The halting rules are:

• Two or more SAEs that are unexpected (in consultation with the sponsor) that are possibly, probably, or definitely related to the study agent(s);

OR

• Two or more subjects experience the same or similar grade 3 or greater AEs that are unexpected and possibly, probably, or definitely related to a study agent;

OR

 Any safety issue that the PI or the CSO determines should halt the study. The DSMB may recommend a halt to the CSO.

In addition, the FDA or any regulatory body having oversight authority may halt the study at any time.

8.4.7.1 Reporting a Study Halt

If a halting criterion is met, a description of the AE(s) or safety issue must be reported by the PI within 1 business day to the CSO and the IRB according to their requirements. The PI will also notify the DSMB.

8.4.7.2 Resumption of a Halted Study

The CSO, in collaboration with the PI, DSMB, and FDA (if applicable), will determine if study activities, including enrollment, study agent administration, and/or other study interventions, may be resumed and any additional modifications or requirements that may apply.

The CSO or sponsor designee will notify the PI of the decision. The PI will notify the IRB of the decision according to the IRB's process.

8.4.7.3 Discontinuation of Study Agent

Subjects who received study agent/intervention/treatment will continue to be followed for protocol-specified safety assessments or as clinically indicated, whichever is more conservative, during a halt.

8.5 UNANTICIPATED PROBLEMS

8.5.1 Definition of Unanticipated Problems

The definition of a UP is provided in section 8.4.1.

8.5.2 Unanticipated Problem Reporting

The investigator will report UPs to the NIH IRB according to NIH Human Research Protections Program (HRPP) Policy 801.

8.5.3 NIH Intramural IRB Reporting of IND Safety Reports

Only IND Safety Reports that meet the definition of a UP will need to be reported to the NIH IRB.

8.6 ADDITIONAL REPORTING REQUIREMENTS

8.6.1 Reporting to the NIH IRB

Non-compliance and other reportable events will be reported to the NIH IRB according to HRPP Policy 801.

8.6.2 Reporting to the NIAID Clinical Director

The PI will report UPs, major protocol deviations, and deaths to the NIAID clinical director according to institutional timelines.

9 STATISTICAL CONSIDERATIONS

9.1 STATISTICAL HYPOTHESIS

The primary hypothesis of this study is that IN or IM BPL-1357 will be well tolerated with minor side effects.

9.2 SAMPLE SIZE DETERMINATION

There will be 15 participants in each treatment group. The study will have adequate power to observe safety signals as defined by the 2 pausing criteria.

 A subject experiences an SAE that is unexpected (per the investigator's brochure or product label) and possibly, probably, or definitely related to a study agent or route of administration;

• A subject experiences two grade 3 or greater AEs that are unexpected (per the investigator's brochure or product label) and possibly, probably, or definitely related to a study agent or route of administration.

Table 7 gives the probability of meeting either criteria in just one arm under various true rates. The table shows that if the true rate in a single vaccine arm is 15% there would be a high probability of detecting the safety signal (power of 0.913). If we meet pausing criteria in both arms, then we also meet halting criteria for study.

Table 8. Probability of meeting pausing criteria

True rate of pausing	Probability of pausing
criteria 1 or 2 (%)	(≥ 1/15)
5%	0.537
10%	0.794
15%	0.913

We will also compare AE rates for the combined vaccine arms to the placebo arm at V_2D28 . We will use a 1-sided .05 level test for the comparison of proportions. With this test we will have 80% power if the true rate in the placebo arm is 5% and the true rate in the vaccine arms is 36%. We will also have 80% power if the true rate in the placebo arm is 10% and the true rate in the vaccine arms is 44%. (This calculation was performed using the SWOG statistical tool website with no continuity correction).

For the safety secondary objective we will compares AE rates in a similar manner but at the end of study, V_2D182 . For the immunogenicity secondary objective, we will compare antibodies against H1, H3, H5, H7, N1, N3, N8, and N9 from both blood and mucosal samples between all 3 arms at V_2D28 . With 15 participants in each arm there will be power of 0.82 to detect an effective size of 1.25 (the effective size is the mean/std) using a two-sided 0.05/3=.0167 level t-test. The level of the test has been adjusted to control for the 3 comparisons between all groups. A similar analysis will be performed at other timepoints for one of the exploratory objectives.

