8.4.6 Pausing Rules for the Protocol

"Pausing" is discontinuation of study intervention/treatment/dosing (agent/placebo/procedure, etc) in a protocol-defined dose group or "arm" at the discretion of the sponsor until a decision is made to either resume or permanently discontinue such activity. The IM or IN route of study agent administration may be paused at the discretion of the DSMB who will not be blinded. The investigators will continue to be blinded as to which study arm is paused. Subjects will continue to be followed for safety during a pause.

The pausing criteria for a group of subjects in this study include any one or more of the following:

- A subject experiences an SAE that is unexpected (per the investigator's brochure or product label) and possibly, probably, or definitely related to a study agent or route of administration;
- A subject experiences two grade 3 or greater AEs that are unexpected (per the investigator's brochure or product label) and possibly, probably, or definitely related to a study agent or route of administration.

The PI or the CSO may also pause dosing/study interventions for one or more subjects for any safety issue. The DSMB may recommend a pause to the CSO.

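### Section 9.2 says that pausing criteria met in both vaccine arms also meet the halting criteria, but no rule in 8.4.7 makes this so

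*Combined protocol and SAP*

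**What the plan says.** Section 9.2 bases its safety-signal power on the two pausing criteria and then adds, without qualification: "If we meet pausing criteria in both arms, then we also meet halting criteria for study". In context the arms are the two BPL-1357 arms, IM and IN.

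The pausing criteria are in 8.4.6, and either is enough. Criterion 1 is one subject with one unexpected, related SAE. Criterion 2 reads "A subject experiences two grade 3 or greater AEs that are unexpected", again with at least a possible relationship. It does not require the two AEs to resemble each other, or to resemble an AE in anyone else.

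The halting rules are in 8.4.7. Two are numerical. The first begins "Two or more SAEs that are unexpected (in consultation with the sponsor" and goes on to require at least a possible relationship to the study agent(s). The second reads "Two or more subjects experience the same or similar grade 3 or greater AEs that are unexpected", with the same relatedness condition. The third is discretionary: any safety issue for which the PI or the CSO decides on a halt. None refers to pauses in both arms.

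Section 8.4.6.2 leaves the step from pause to halt to the CSO, working with the PI and DSMB, who determine "whether the events that triggered the pause require expansion to a study halt".

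**The concern.** Pausing criterion 2 and the second halt rule count different things. The first counts AEs within one subject and ignores their type. The second counts subjects and requires their AEs to match. One triggering subject in each vaccine arm therefore need not satisfy any numerical halt rule, although 9.2 says that the halting criteria are met.

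An IRB, DSMB or regulator reading the statistical section would credit the trial with a stopping property that its stopping rules lack. Staff who face a mixed pair of triggers would find that 9.2 says the halting criteria are met and 8.4.7 does not.

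**Working it through.** **Inputs.** 15 participants per arm and true rates of 5%, 10% and 15% (9.2, Table 8); the pausing criteria (8.4.6); the halting rules (8.4.7).

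**1. Reproduce Table 8.** The probability that at least one of 15 subjects triggers is 1 − (1 − p)^15.

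- p = 0.05: 1 − 0.95^15 = 0.537
- p = 0.10: 1 − 0.90^15 = 0.794
- p = 0.15: 1 − 0.85^15 = 0.913

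All three match the table.

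**2. How often the sentence would come into play.** Assume the same rate in both vaccine arms and independent arms. The probability that both trigger is the square of the unrounded value: 0.5367² = 0.288, 0.7941² = 0.631 and 0.9126² = 0.833. At the plan's own planning rates this is not a remote event.

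**3. Test the implication.** Take one triggering subject per vaccine arm, with criterion 2 met through non-serious AEs.

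| IM arm trigger | IN arm trigger | SAEs | SAE halt rule | Matching-AE halt rule |
|---|---|---|---|---|
| SAE | SAE | 2 | met | not needed |
| SAE | criterion 2 | 1 | not met | only if the two subjects' AEs match |
| criterion 2 | SAE | 1 | not met | only if the two subjects' AEs match |
| criterion 2 | criterion 2 | 0 | not met | only if the two subjects' AEs match |

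Only one of the four combinations guarantees a numerical halt. A single counterexample is enough to defeat the sentence: one subject per arm, each with two non-serious grade 3 AEs, and none alike across the two subjects.

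**4. Can the share of such cases be sized?** It depends on two quantities that the documents do not give: s, the share of triggering subjects who trigger through an SAE, and q, the chance that the subjects' grade 3 or greater AEs match. If s = 0 and q = 0, no double trigger meets a numerical halt rule. If s = 1, every one does. With one triggering subject per arm, q = 1 also means that every one does. The range is therefore 0 to 1.

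Values in between also depend on how many subjects trigger. Take s = 0.5 and q = 0 as an assumption, with one SAE per SAE-triggering subject:

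- Exactly one triggering subject per arm: share without a numerical halt = 1 − 0.5² = 0.75.
- Any number of triggering subjects: let a = p·s, P0 = (1 − a)^15 − (1 − p)^15 (arm triggers, no SAE) and P1 = 15a(1 − a)^14 (exactly one SAE). The share is (P0² + 2·P0·P1) / [1 − (1 − p)^15]². This gives 0.165/0.288 = 0.57 at 5%, 0.255/0.631 = 0.40 at 10% and 0.218/0.833 = 0.26 at 15%.

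The spread from 0.26 to 0.75 under a single choice of s and q shows why no one figure should be quoted.

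**The case against.** The strongest reply is that nothing operational rests on this sentence. It is a remark in a sample-size section, and no sample size, test or power figure uses it. Sections 7.1 and 10.2 send readers to section 8.4 for the pausing and halting rules. Oversight is also close. A met pausing criterion is reported to the CSO and IRB within 1 business day (8.4.6.1). The PI obtains a DSMB recommendation (8.4.5.3.1), and the DSMB can act by route: "The IM or IN route of study agent administration may be paused at the discretion of the DSMB who will not be blinded". The PI or CSO may halt for any safety issue. Every group receives both routes (6.1.2), so pausing both would stop dosing in all groups. Because enrollment and first vaccination share the V1D0 visit, no new participant could then be dosed either.

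Most of this stands, and it makes the practical gap small. It does not rescue the sentence. Saying that the criteria are met is different from saying that someone may decide to halt, and 8.4.6.2 treats expansion to a halt as an open decision. Suspension of enrollment is part of the definition of a halt in 8.4.7 but not of a pause in 8.4.6.

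A reader might infer two stronger points that the documents do not support.

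- *A double trigger could go unmanaged.* The reporting and review steps above rule this out.
- *Even two SAEs might not meet the halt rule.* Pausing counts events "possibly, probably, or definitely related to a study agent or route of administration", while the SAE halt rule says "possibly, probably, or definitely related to the study agent(s" and omits route. But 8.4.3.1.2 grades causality only against the study agents and has no separate route category. An SAE from giving the agent by a route would ordinarily be graded as agent-related. The difference in wording is too thin to rely on.

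**Conclusion.** The concern holds on the wording. The 9.2 sentence is unqualified and does not follow from 8.4.7: both vaccine arms can trigger without any rule-based halt, which is then left to the CSO, PI and DSMB. This conclusion needs no assumption about rates.

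The both-arm probabilities (0.288, 0.631 and 0.833) rest on equal rates and independent arms. They say how often the sentence would be invoked, not how often it would be wrong. A reader might infer from a simple one-subject-per-arm calculation that most double triggers, such as 0.75 of them, escape a halt. The documents give neither the SAE share nor the AE similarity that such a figure needs, so it should not be used.

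Table 8 and the existing thresholds are unaffected. The mismatch should be corrected because 9.2 credits the trial with a stopping property that the rules lack, but the practical consequence is limited.

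**What to change.** Make the two sections agree. Which way depends on what the sponsor intends.

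- **If 9.2 states the intended rule**, add to 8.4.7: *Pausing criteria are met in both the IM and IN BPL-1357 arms, as identified by the unblinded DSMB and reported to the CSO.* The cost is small: the study might halt temporarily for unrelated events, and the blinded team would learn that both vaccine arms were involved, whereas 8.4.6 keeps investigators blinded to which arm is paused.
- **If it does not**, reword 9.2: *If pausing criteria are met in both arms, halting criteria are also met when there are two or more unexpected related SAEs, or the same or similar unexpected related grade 3 or greater AEs in two or more subjects; otherwise expansion to a halt is decided under 8.4.6.2.* This has no operational cost. It leaves mixed or dissimilar triggers to case-by-case review, as the current rules already do.

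Either change is one line and needs no recalculation.

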3 OBJECTIVES AND ENDPOINTS

Table 2: Objectives and Endpoints

OBJECTIVES	ENDPOINTS	JUSTIFICATION FOR ENDPOINTS	
Primary			
To assess the safety of BPL-1357 given IM or IN, compared to placebo.	 a. Type and severity (by grading) of AEs through day V₂D28. b. Type of SAEs through day V₂D28. 	The standard way to determine safety is to evaluate AE incidence and severity.	
Secondary			
 To further assess the safety of BPL-1357 given IM or IN, compared to placebo. To assess the immunogenicity of BPL- 	Type and severity (by grading) of AEs through day V ₂ D182.	Analysis of antibody titers will enhance our understanding of the immune response to BPL-1357.	

OBJECTIVES	ENDPOINTS	JUSTIFICATION FOR ENDPOINTS
1357 given IM or IN, compared to placebo.	 b. Type of SAEs through day V₂D182. 2. Immunogenicity c. Antibodies against H1, H3, H5, and H7 head and stalk as measured by HAI or ELISA from blood and mucosal samples at V₂D28. d. Antibodies against N1, N3, N8, and N9 as measured by NAI or ELISA from blood and mucosal 	
	samples at V ₂ D28.	
Tertiary/Exploratory		
 To characterize the systemic and mucosal immune responses induced by BPL-1357 given IM or IN, compared to placebo. To further characterize the immune response induced by BPL-1357 given IM or IN through variable, diversity, and joining (VDJ) gene repertoire analysis, cytokine analysis, cytometry, transcriptomics, and assessment of T-cell responses. To assess the rates of influenza disease among groups given IM or IN BPL-1357 compared to placebo. 	 Antibodies against H1, H3, H5, and H7 head and stalk as measured by HAI or ELISA from blood and mucosal samples at V₁D7, V₁D14, V₁D28, V₂D7, V₂D14, V₂D56, and V₂D182. Antibodies against N1, N3, N8, and N9 as measured by NAI or ELISA from blood and mucosal samples at V₁D7, V₁D14, V₁D28, V₂D7, V₂D14, V₂D56, and V₂D182. VDJ gene repertoire analysis. Cytokine analysis. Flow cytometric phenotyping of lymphocytes. Transcriptomic gene expression. T-cell responses. 	Additional analysis of antibody titers will further enhance our understanding of the immune response to BPL-1357. VDJ gene repertoire analysis, cytokine analysis, flow cytometry, transcriptomic analysis, and analysis of T-cell activity may help identify other possible correlates of protection for influenza after vaccination, such as innate and other cellular responses. Rates of influenza disease among groups may provide additional data regarding vaccine-associated immunity

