6.3 MEASURES TO MINIMIZE BIAS: RANDOMIZATION AND BLINDING

6.3.1 Randomization

Participants will be randomized at enrollment in a 1:1:1 ratio to treatment groups A, B, and C. Randomization will occur using computer-generated randomization codes. This code will be sent to the pharmacy where the unblinded pharmacist will have the key and prepare the appropriate agent for administration. The randomization code list will be maintained by the Investigational Drug Management Research Section (IDMRS) in the electronic Investigational Drug Management System (IDMS).

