9.3 POPULATIONS FOR ANALYSES

Safety will be evaluated with intention-to-treat analysis comparing IN vs IM routes. All subjects receiving the vaccine will be included in the analysis.

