9.3.1 Evaluable for Toxicity

All participants will be evaluable for toxicity from the time of their first treatment with BPL-1357 or placebo.

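### Sections 9.2, 9.3 and 9.4 do not agree on the primary safety contrast, and no route-versus-placebo adverse-event test is named or powered

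*Combined protocol and SAP*

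**What the plan says.** The primary objective in section 3 (Table 2) is "To assess the safety of BPL-1357 given IM or IN, compared to placebo". Four places in section 9 then bear on how safety is compared.

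- **9.2 Sample Size Determination.** "We will also compare AE rates for the combined vaccine arms to the placebo arm at" V2D28. On level and sidedness: "We will use a 1-sided .05 level test for the comparison of proportions". On power: "80% power if the true rate in the placebo arm is 5% and the true rate in the vaccine arms is 36" per cent, with the same power for 10% against 44%. The secondary safety comparison at V2D182 follows the same pattern. Separately, Table 8 gives a per-arm probability of meeting the pausing criteria.
- **9.3 Populations for Analyses.** "Safety will be evaluated with intention-to-treat analysis comparing IN vs IM routes". The next sentence describes the analysed set as the subjects who get the vaccine.
- **9.3.1 Evaluable for Toxicity.** "All participants will be evaluable for toxicity from the time of their first treatment with BPL-1357 or placebo".
- **9.4.1 and 9.4.2.** Events are tabulated by group, tests of proportions are run between groups, and 90% confidence intervals are given. The pairs of groups, the level and the sidedness are not stated. One related serious event in an arm meets the primary safety endpoint for that arm.

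Section 8.4.4.2 removes participants who withdraw before dosing and puts everyone exposed to study agent in the safety dataset.

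**The concern.** Two contrasts are spelled out: vaccine by either route pooled against placebo (9.2), and one route against the other (9.3). Neither compares a single route with placebo. Taken literally, 9.3 has no placebo comparator, which conflicts with 9.3.1 and with the objective. Its intention-to-treat label also sits badly with 8.4.4.2, which drops undosed participants. For antibodies, by contrast, 9.2 and 9.4.2 specify all three pairwise comparisons and a level of 0.05/3, so the gap is specific to safety.

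Two things are at stake. An undefined primary contrast can be chosen after unblinding. And the pooled test averages the two routes, so an excess in one route is diluted by the other. A non-significant pooled result could then be read as support for the hypothesis that IN or IM vaccine is well tolerated, although neither route was tested against placebo by itself.

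**Working it through.** **Inputs.** "There will be 15 participants in each treatment group" (9.2); "Participants will be randomized at enrollment in a 1:1:1 ratio to treatment groups A, B, and C" (6.3.1). Pooling therefore gives 30 against 15. The test is one-sided at 0.05 (critical value 1.645) without continuity correction, and the rates are those in 9.2.

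**Formula (normal approximation).** With placebo rate p0 on n0 participants and vaccine rate p1 on n1:

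- s0 = √[p̄(1−p̄)(1/n0 + 1/n1)], where p̄ is the overall rate
- s1 = √[p0(1−p0)/n0 + p1(1−p1)/n1]
- power = Φ{[(p1−p0) − 1.645·s0]/s1}

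The exact figures sum binomial probabilities over every outcome for which the same uncorrected pooled-variance z-statistic exceeds 1.645.

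**Step 1: the plan's own figure, 5% against 36%, 30 against 15.** p̄ = (15×0.05 + 30×0.36)/45 = 0.2567; s0 = 0.1381; s1 = 0.1041. Power = Φ[(0.31 − 0.2272)/0.1041] = Φ(0.795) = 0.787; exact 0.813. For 10% against 44%: 0.790; exact 0.798. The stated 80% reproduces. A two-sided test (0.647, 0.660) does not match, nor does 15 against 15 (0.690, 0.688).

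**Step 2: only one route raised, the other at the placebo rate.** The combined vaccine rate is (0.05 + 0.36)/2 = 0.205. Then p̄ = 0.1533; s0 = 0.1139; s1 = 0.0927. Power = Φ[(0.155 − 0.1874)/0.0927] = Φ(−0.350) = 0.363. For 10% and 44% the combined rate is 0.27 and power is 0.350. The exact calculation, with each vaccine arm as its own binomial, gives 0.412 and 0.359.

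**Step 3: other route at half the excess** (20.5% or 27%). Exact power is 0.635 and 0.594.

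**Step 4: the affected route against placebo, 15 against 15.** p̄ = 0.205; s0 = 0.1474; s1 = 0.1361. Power = Φ[(0.31 − 0.2425)/0.1361] = Φ(0.496) = 0.690; exact 0.754. For 10% against 44%: 0.688; exact 0.738.

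| Scenario (exact power) | 5% / 36% | 10% / 44% |
|---|---|---|
| Pooled, both routes raised | 0.81 | 0.80 |
| Pooled, second route at half the excess | 0.64 | 0.59 |
| Pooled, one route raised only | 0.41 | 0.36 |
| Affected route against placebo | 0.75 | 0.74 |

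**Step 5: per-route rate that gives 80% power, 15 against 15.** Exact: about 38.5% against 5% and 48% against 10%. Normal approximation: about 42% and 50%.

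**Step 6: error rate of two unadjusted tests sharing one placebo arm.** Let a(i) be the chance that one route is significant when placebo has i events. The familywise rate is Σ P(i)·[1 − (1 − a(i))²]. With all arms at the same rate this is 0.033 at 5% and 0.079 at 10%.

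**The case against.** The strongest reply is that the pooled test is an addition, not the whole safety analysis. Section 9.2 introduces it as something also done, after a per-arm justification: Table 8 gives 0.913 for a 15% rate in a single arm. Section 9.4.2 has a per-arm rule for related serious events. Sections 9.4.1 and 9.4.2 plan tables by group, between-group tests and confidence intervals, which would naturally include each route against placebo. All of that stands. A reader might infer that the trial as a whole would find a one-route reaction with only 36-41% power, and the documents do not support that: the figure belongs to one test. What the reply does not supply is a named pair, level or power for any route-versus-placebo test. The pausing criteria cover only unexpected, related serious or grade 3 or greater events, not adverse-event rates in general.

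A reader might also infer that the stated 80% is wrong. It is not. It is stated for a rate shared by the vaccine arms, and it reproduces.

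Nor do the documents show that a one-route excess is the likely pattern. Of the 18 non-serious risks listed for IM in 2.3.1.1, 17 also appear for IN; one is IM-only and five are IN-only. Every participant receives something by both routes, and 2.3.1.2 says that saline by either route can cause local reactions. A one-route excess is plausible for those local items, no more.

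Finally, the objective can be read as vaccine by either route against placebo, which the pooled test would answer. That reading is open, but it still does not fit 9.3.

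**Conclusion.** The inconsistency is real and should be fixed. Sections 9.2, 9.3 and 9.4 give three different accounts of the safety comparison, and none of them names each route against placebo. The power consequence is conditional. The 80% needs both routes to share the raised rate; it falls to about 41% or 36% if one route is at 36% or 44% and the other is exactly at the placebo rate, and to about 64% or 59% if the other route has half the excess. A route-specific test would have about 69-75%, the range reflecting normal against exact calculation and the two scenarios. These figures assume 15 participants analysed per group and the uncorrected one-sided 0.05 test. The population conflict in 9.3 is smaller, because 8.4.4.2 and 9.3.1 already point to the right set. With by-group tabulation and per-arm rules in a 45-person phase 1 trial, this does not undermine the design.

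**What to change.** - **9.2 and 9.4.2.** Name group A versus group C and group B versus group C as the primary safety contrasts, each with the difference in proportions, its 90% confidence interval and the one-sided 0.05 test. Make combined vaccine versus placebo, and A versus B, supportive. Carry the same structure to V2D182.
- **9.3.** Replace the intention-to-treat, IN-versus-IM sentence with one safety population: all participants who receive any study agent, vaccine or placebo. This agrees with 8.4.4.2 and 9.3.1.
- **Power statement.** Give the per-route rates for 80% power as about 38.5% against 5% and 48% against 10% (exact), or about 42% and 50% (normal approximation, the closer in kind to the uncorrected calculation in 9.2). Say which method is used.
- **Multiplicity.** State that the two one-sided 0.05 tests are unadjusted, with a familywise error of about 3% at a 5% event rate and 8% at a 10% rate.

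No participants or procedures are added. The cost is a less favourable detectable rate than the pooled 36% and 44%, and two tests in place of one.
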